8.1.3. Rationale for Study Design: Safety Evaluation Study

The AESIs included in this study are considered as potential or identified safety risks following administration of Ad26.COV2.S. The selected AESIs represent a heterogeneous group including multiple organ systems, and acute and chronic conditions (Section 8.3.3).

The SCRI design has been selected as the primary design for acute events (i.e., AESIs expected to occur within a disease risk window of 60 days) because it only includes vaccinated individuals, which avoids misclassification of unexposed status due to incomplete capture of vaccinations in some of the electronic health care databases. Because it uses each individual as its own control, the SCRI design avoids potential confounding by factors that do not vary with time. To account for the possibility that increased risks of AESIs might extend beyond the control interval, the control and risk windows are separated by a buffer period to minimise potential of capturing prevalent events in the risk window (length to be defined in SAP). Although most AESIs are age-dependent, confounding by age is not anticipated because the follow-up period is short compared with the age effect on the incidence of AESIs. However, because the SCRI design generally has less statistical power and for some AESIs may be subject to confounding by other time-variant confounders such as seasonality (a proxy for respiratory infections), a cohort design will be used in sensitivity analyses of acute events, with matching on calendar time and other key variables.

Because the SCRI design is not appropriate for non-acute events, the cohort design will be used to assess these types of events (i.e., AESIs expected to occur within a disease risk window of more than 60 days). Some of the participating data sources may not have complete information on COVID-19 vaccination (e.g., PHARMO) and therefore risk misclassification of the non-exposed group (these may have been vaccinated). In a sensitivity analysis, these will be excluded to investigate the impact of misclassification of exposure in the non-exposed group on the pooled analysis of non-acute events.

Disease-specific risk windows have been defined for all AESIs; however, these risk windows are based on currently available evidence or best estimates (e.g., from recent post-marketing use, experience with other marketed vaccines or knowledge of COVID-19 or case reports) and may not be strictly applicable to the Ad26.COV2.S vaccine. For this reason, sensitivity analyses with extended risk windows will be considered in the SCRI study for outcomes that do not have a well-defined risk interval (to be defined in SAP). For these events, a descriptive time-to-onset analysis will be conducted during a period up to one year after the Ad26.COV2.S vaccine to inform the risk interval for the sensitivity analysis.

8.2. Setting and Study Population

8.2.1. Study Setting

For the implementation of the feasibility assessment, electronic health care databases in Southern and Western Europe that have shown interest and are members of the Vaccine Monitoring Collaboration for Europe (VAC4EU) will be used. The selected data sources and two-letter country codes are as follows:

- SIDIAP (Sistema d'Informació per el Desenvolupament de la Investigació en Atenció Primària) [Information System for Research in Primary Care] (ES)
- VID (La Fundació para el Fomento de la Investigación Sanitaria y Biomédica de la Comunitat Valenciana) [The Foundation for the Promotion of Health and Biomedical Research of Valencia Region] (ES).
- PHARMO DATABASE NETWORK (PHARMO Institute for Drug Outcomes Research) (NL)
- ARS Toscana (Agenzia Regionale di Sanità della Toscana) [a research institute of the Tuscany region of Italy] (IT)]. Since the approval of protocol version 2 by the EMA PRAC, a revision of the procedure for data access in the Tuscany Region has started. Hence, the study team at ARS Toscana has suspended its activities concerning the re-use of data until the revision of the procedures is complete. Until then ARS Toscana cannot contribute data to the study.

Further information on the data sources used in this study can be found in Section 8.4. When needed (based on specific safety concerns occurring in specific countries, or because of size) additional data sources may be added for dedicated evaluation studies, if they have adequate data on exposure, outcomes and covariates.

8.2.2. Source Population

The source population will be made up of all individuals registered in each of the participating health care data sources.

8.2.3. Study Duration and Follow-Up

Feasibility Assessment

For the feasibility assessment, the study period will start on the date when each participating country begins with the Ad26.COV2.S vaccine or the latest date when the individual is registered in the data source (plus 365 days) or born and will end a maximum of 12 months thereafter. Individuals will be followed until the earliest of the following dates: death, end of data availability, individual exit from the data source, or the completion of the period.

Safety Evaluation Study

- For the SCRI design, the study period will start at the date of the start of the pre-vaccination control window (Table 1). Follow-up ends at the earliest of the following: death, end of data availability, individual withdrawal of the study, end of the post-vaccination risk or control window, or receipt of another COVID-19 vaccine. In a sensitivity analysis, follow-up will be censored upon receipt of other vaccines (non-COVID-19 vaccine). We will also compare the Ad26.COV2.S vaccine with active comparators with 1) only 1-dose strategy and 2) a 2-dose strategy. Figure 1 shows the different periods considered for the SCRI design.
- For the cohort design, the study period will start at the date when each participating country will begin with the Ad26.COV2.S vaccine and will end at the end of data availability at each data source. For the cohort design, the follow-up will start at the beginning of the vaccination risk window, as detailed in Table 1 and ends at the occurrence of each AESI, death, end of data availability, individual exits the database, after one year of follow-up, receipt of a

COVID-19 vaccine (unexposed cohort only), receipt of a different COVID-19 vaccine from the one granting access to the study (exposed cohorts only). For the vaccine-exposed comparator groups, a second dose of the same corresponding vaccine will be allowed (more details will be provided in the SAP). In a sensitivity analysis, follow-up in the cohort study will be censored upon receipt of other vaccines (non-COVID-19 vaccine). Another sensitivity analysis will also compare the Ad26.COV2.S with active comparators with (1) a 1-dose strategy and (2) a 2-dose strategy. For the subgroup analysis of subjects without COVID-19 at the start of risk window, patients will be censored if they develop COVID-19 during follow-up.

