The sponsor has created a list of AESIs based on current knowledge of the Ad26.COV2.S vaccine. Background incidence rates for most of the data sources and AESIs are available on the VAC4EU dashboard <https://vac4eu.org/covid-19-tool/>. Definitions and codes are available on Zenodo (<https://zenodo.org/communities/vac4eu/>).

Covariate definition

Feasibility Assessment

In the feasibility assessment, covariates will be assessed at the time of COVID-19 vaccine administration (index date).

Safety Evaluation Study

For the cohort analysis, covariates for the study populations will be defined at the index date. For the SCRI design, time-varying covariates will be identified both at the start of the risk window and the control window.

Covariates will be used to define and describe the study cohorts and populations of special interest and their baseline characteristics and/or to control for confounding. Additional covariates may be added during the conduct of the study if deemed important. The look-back observation period to define covariates of interest will be all available information before the index date in each data source with a minimum of 12 months, except when an alternative look-back window is specified.

Data Sources

The study will use data from secondary electronic health record databases that are population-based. All data sources will have the ability to provide data on COVID-19 vaccines, outcomes (diagnoses, procedures, laboratory results, and treatments), and important covariates. It is not currently known the extent to which COVID-19 vaccines, product types, and batch numbers will be captured in data sources. To be included in the study, data sources should preferably be updated at a minimum once every 3 months. At the proposal stage, members of VAC4EU were offered the option to participate in the study. Four data sources from 3 countries (Spain, the Netherlands and Italy) will be included in the study. A more detailed description will be included in the VAC4EU FAIR Catalogue.

When establishing the agreements with the data sources to conduct the study, it will be emphasized that the current list of AESIs may be expanded during the course of the study to accommodate newly identified AESIs.

Study Size

The study will be conducted in a source population of approximately 18.1 million individuals, although children will not be vaccinated. It is assumed that up to 10% will be vaccinated with the Ad26.COV2.S vaccine.

Main Statistical Methods

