8.2.4. Inclusion Criteria

8.2.4.1. Feasibility Assessment

For the feasibility assessment, the individual will be included if there is at least one day of follow-up and the individual has at least 12 months of data in the data source at the index date.

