8.7.1.1. Feasibility Analysis

Demographic and Baseline Characteristics

The distributions of baseline characteristics at start of COVID-19 vaccination for each COVID-19 vaccine exposure group will be calculated to describe differences between the groups. For continuous variables, means, standard deviations, medians, and other quartiles will be estimated. For categorical variables, counts and proportions will be estimated. The missingness of variables will also be described.

Vaccine uptake

For every data source, the number of administered doses per COVID-19 vaccine brand within the primary series (dose 1 and dose 2) will be calculated by calendar time (in months) over the follow-up period.

For individuals with a given year of birth vaccination uptake for dose 1 over time will be calculated. The coverage at month i for birth year j is calculated by dividing the number of vaccinated individuals n_{ij} by the total number of individuals under follow-up at month i (N_{ij}), expressed as a percentage. Estimates of vaccination uptake will be compared with data provided by ECDC.

Algorithms for outcome definitions

For each outcome, the number of cases by diagnosis code will be counted, and the impact on the case count will be assessed when confirmatory medications /procedures or laboratory tests are used. All such counts will be stratified by meaning (GP record, hospitalisation primary diagnosis, hospitalisation secondary diagnosis).

Time-to-onset

Descriptive analyses of the time-to-onset of event (up to one year after vaccination) may inform the selection of risk intervals for the sensitivity analyses.

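### Feasibility follow-up is capped at 12 months from country rollout, which keeps nearly all vaccinees from reaching the one-year-after-vaccination horizon of the time-to-onset analysis

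*Protocol*

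**What the plan says.** For the feasibility assessment, Protocol section 8.2.3 states that "the study period will start on the date when each participating country begins with the Ad26.COV2.S vaccine". Where a person's birth, or registration plus 365 days, comes after rollout, the later date applies. On the end of the period, the section says that it "will end a maximum of 12 months thereafter". Individuals are followed to the earliest of "death, end of data availability, individual exit from the data source, or the completion of the period". The abstract gives the same rule. None of these starting points is the vaccination date.

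Section 8.7.1.1 (Feasibility Analysis) counts from vaccination instead: "Descriptive analyses of the time-to-onset of event (up to one year after vaccination) may inform the selection of risk intervals for the sensitivity analyses". Section 7 lists time-to-onset among the feasibility objectives. Section 8.1.3 gives the same horizon: "a descriptive time-to-onset analysis will be conducted during a period up to one year after the Ad26.COV2.S vaccine". That section is the rationale for the safety evaluation study, so the direct conflict is between 8.2.3 and 8.7.1.1.

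Under section 8.2.4.1, "the individual will be included if there is at least one day of follow-up" (with 12 months of prior data), so people vaccinated late in the period enter with very little follow-up.

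The safety-evaluation cohort in the same section 8.2.3 has no such cap. Its period runs to the end of data availability, with up to one year of follow-up per person.

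**The concern.** The censoring rule runs on calendar time from rollout and the analysis horizon runs from each dose. A person already eligible at rollout and vaccinated t months later has at most 12 minus t months of observation. Follow-up for the later part of the year therefore comes only from early vaccinees, and the amount lost depends on vaccination date.

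Two uses of the feasibility assessment are exposed. The onset distribution is meant to help choose extended risk windows. Table 5 also uses the assessment for the number of outcomes and time to event. That includes the non-acute events whose Table 1 window is 1-365 days: multiple sclerosis, which section 8.3.2 places in the first report, and autoimmune thyroiditis, type 1 diabetes and acute aseptic arthritis in later reports. For these events a shortened year directly lowers the count on which feasibility is judged.

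An analysis plan cannot repair this by choice of estimator, because the protocol itself excludes the follow-up.

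**Working it through.** The protocol gives no figure to reproduce on this point, so the check is direct arithmetic.

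**Inputs.** From section 8.2.3: a cap of 365 days from rollout for people already registered long enough at that date. From section 8.7.1.1: a horizon of 365 days from vaccination. Assumed, because the protocol gives no uptake curve: vaccination day uniform over U days after rollout, with U = 90, 183 or 270 (about 3, 6 and 9 months); a constant event rate, the same for early and late vaccinees; no vaccine effect; no other censoring.

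**Formulas.**
- Fraction of vaccinees still observed d days after vaccination = min(1, (365 − d)/U). Observation is complete to day 365 − U.
- Mean follow-up = 365 − U/2. Share of one-year person-time lost = (U/2)/365.
- Person-days per vaccinee after day 182.5: for U = 90, mean follow-up minus 182.5; for U = 183 or 270, 182.5²/(2U).

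| | U = 90 | U = 183 | U = 270 |
|---|---|---|---|
| Mean follow-up (days) | 320 | 273.5 | 230 |
| One-year person-time lost | 45/365 = 12% | 91.5/365 = 25% | 135/365 = 37% |
| Person-days after day 182.5 | 137.5 | 33,306/366 = 91.0 | 33,306/540 = 61.7 |
| Share of person-time after day 182.5 (50% if complete) | 137.5/320 = 43% | 91.0/273.5 = 33% | 61.7/230 = 27% |
| Still observed at day 300 | 65/90 = 72% | 65/183 = 36% | 65/270 = 24% |
| Observation complete to day | 275 | 182 | 95 |

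With a constant rate, expected events are proportional to person-time. One-year counts for a 1-365 day event are therefore understated by the same 12%, 25% or 37%. Counting in whole days, the share of vaccinees with a full 365 days is 1/U, which is 1.1%, 0.5% and 0.4%.

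**Does the onset curve become misleading?** A simulation of 2 million people with a constant hazard compared raw counts with rates. With uptake over 180 days, the first-half to second-half ratio of raw onset counts was 2.0; with uptake over 365 days it was 3.1. The corresponding ratio of rates per person-time was about 1.04 in both, against a theoretical value of 1. Front-loading is thus a feature of raw counts and largely disappears once person-time is in the denominator.

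**Are the acute-event windows affected?** Table 5 restricts extended windows to acute events, and the longest acute window in Table 1 is 1-60 days. Observation is complete to day 95 even with nine-month uptake, and to day 182 with six. Over that range even a raw histogram stays flat when there is no effect. With six-month uptake, days 1-60 hold 60/273.5 = 22% of onsets instead of 60/365 = 16%. This comes from a smaller total, not from clustering within the range where a window would be extended.

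**After the fix.** If the 365 days run from each dose, U drops out of the formulas. Everyone can contribute a full year, and the second-half share returns to 50%.

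**The case against.** The strongest reply is that the horizon is worded as a maximum. Staggered entry with administrative censoring satisfies it, and nobody is promised a full year. The analysis is also descriptive, may inform sensitivity windows only, and feeds no primary estimate. This limits the weight of the point. It does not remove it: a maximum that fewer than 2% of vaccinees could reach in the scenarios above is not a workable horizon, and the one-year counts fall short on any reading.

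A reader might infer more than the protocol supports, in three ways.

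- *That the onset curve will look front-loaded without any vaccine effect.* This requires raw onset counts. The protocol does not specify them, and section 7 lists incidence rates and cumulative incidence with confidence intervals among the feasibility endpoints.
- *That extended risk windows will be chosen too short.* These windows concern acute events, and in the three scenarios in the table observation is complete well past day 60.
- *That nobody except those vaccinated on rollout day can be followed for a year.* This ignores the later starting point for people whose registration plus 365 days falls after rollout. Their clock starts later, though still not at vaccination.

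One caution applies to the reassurance about rates. It assumes that early and late vaccinees have the same event rate. Section 8.9 describes most roll-out strategies as age-based, and section 8.1.3 says most of the events depend on age, so the people behind the late part of the curve may differ from those behind the early part. The documents do not allow this to be sized.

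**Conclusion.** The point holds as an inconsistency between a stated censoring rule and a stated horizon, with a moderate cost. Under assumed uniform uptake over 3, 6 or 9 months and a constant rate, 12%, 25% or 37% of one-year person-time is lost and the second-half share falls to about 43%, 33% or 27%. The consequences are a thin late tail in the onset curve and understated one-year counts for the non-acute events. The primary windows in Table 1 are untouched, the extended windows for acute events are little affected, and a biased onset curve is not established. The sizes depend on uptake timing, which the protocol does not give. It should be corrected, but no primary result rests on it.

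**What to change.** In section 8.2.3 and the abstract, for the incidence and time-to-onset parts of the feasibility assessment, end follow-up 365 days after each person's own vaccination, or at earlier death, exit from the data source or end of data. In section 8.7.1.1, state that onset will be reported as rates per person-time or as censoring-adjusted cumulative incidence, with the number still observed at each time.

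The cost is about one sentence in each place and no extra extraction. Section 8.1.1 has the second feasibility report and the final report share one extraction, and section 5 plans it for Q1-Q2 2023. Section 8.4.3 records Ad26.COV2.S doses in the Netherlands by 8 May 2021, so much of the missing follow-up should already be in that extraction, subject to each source's data lag. Section 5 gives the first feasibility report an actual date of 10 November 2022, so the change would apply to the second report.

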For the feasibility assessment, the study period will start on the date when vaccination with Ad26.COV2.S began in each participating country or the latest date when the individual is registered in the data source (plus 365 days) or born and will end a maximum of 12 months thereafter. Individuals will be followed until the earliest of the following dates: death, end of data availability, individual exit from the data source, or the completion of the period.

Safety Evaluation Study

- For the SCRI design, follow-up starts at the start of the pre-vaccination control window following an AESI specific washout period. Follow-up ends at the earliest of the following: death, end of data availability, individual withdrawal of the study, end of the post-vaccination risk or control window, or receipt of another COVID-19 vaccine. We will compare the Ad26.COV2.S vaccine with active comparators with 1) only 1-dose strategy and 2) a 2-dose strategy.
- For the cohort design, the study period will start at the time when Ad26.COV2.S vaccination starts in each participating country and will end at the end of follow-up. For the cohort design, follow-up starts at the start of each risk window and ends at the occurrence of each AESI, death, end of data availability, individual exits the database, after one year of follow-up, receipt of a COVID-19 vaccine (unexposed cohort only), receipt of a different COVID-19 vaccine from the one granting access to the study (exposed cohorts only). For the vaccine-exposed comparator groups, a second dose of the same corresponding vaccine will be allowed (more details will be provided in the SAP). In a sensitivity analysis, follow-up in the cohort study will be censored upon receipt of other vaccines (non-COVID-19 vaccine). We will compare the Ad26.COV2.S vaccine with active comparators with 1) only 1-dose strategy and 2) a 2-dose strategy. For the subgroup analysis of subjects without COVID-19 at the start of each risk window, patients will be censored if they develop COVID-19 during follow-up.

Variables

Exposure assessment

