7. RESEARCH QUESTION AND OBJECTIVES

Research Question

This study has 2 chronologically consecutive aims: 1) to conduct a feasibility assessment aiming to inform the safety evaluation study and 2) to assess the risk of developing pre-specified and newly identified AESIs following administration of Ad26.COV2.S.

Objectives

Feasibility Assessment

The feasibility assessment will include the following objectives (not all objectives may be assessed in all analyses):

- To provide a comprehensive overview of the methods for identification of COVID-19 vaccine exposure including provenance of data and linkage to vaccination registry
- To monitor the number of individuals exposed to any COVID-19 vaccines (Ad26.COV2.S, Vaxzervria vaccine and mRNA COVID-19 vaccines) and to investigate the risk of misidentification of the COVID-19 vaccine exposure. Both missing vaccination instances and misclassification of the type of vaccine will be assessed with the benchmark provided by the ECDC: <https://vaccinetracker.ecdc.europa.eu/public/extensions/COVID-19/vaccine-tracker.html#uptake-tab>)
- To compare individuals receiving different COVID-19 vaccines with respect to demographics and clinical characteristics of recipients, potential confounders and risk factors for the AESI
- To conduct time-to-onset analyses for the sponsor prioritised AESIs (including exacerbation of asthma) with respect to time since vaccination and without prespecified risk windows
- To describe booster vaccine doses in individuals who received a first dose of Ad26.COV2.S.

The joint evaluation of the objectives mentioned above will inform on the overall feasibility of the study.

Safety Evaluation Study

Primary objective

The primary objective of this safety evaluation study is to assess the potential association between the occurrence of predefined and newly identified AESIs and vaccination with Ad26.COV2.S compared to individuals unexposed to any COVID-19 vaccine, and to individuals exposed to other types of COVID-19 vaccines (mRNA or adenovirus platforms) within disease-specific risk periods, and among the vaccinated, to a control window within the same individual.

Secondary objectives

The secondary objectives of this study are to assess the potential association between the occurrence of predefined and newly identified AESIs and vaccination with Ad26.COV2.S in the following specific subpopulations (part of the main study population):

-
- Immunocompromised individuals,
 - Pregnant women,

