[Figure 1](#) shows the SCRI study design diagrammatically using an example with a risk window and control window of 42 days.

Figure 1: Self-Controlled Risk Interval Design

T is time and T=0 is the index date.

8.1.2.2. Cohort Design (Primary Study Design for Non-acute Events and Sensitivity Analysis Design for Acute Events)

For the primary analysis of non-acute events, a retrospective cohort design will be used to estimate the rate of vaccination with Ad26.COV2.S vaccine, describe the characteristics of these vaccinated individuals and subsequently to estimate the incidence of new-onset autoimmune thyroiditis, multiple sclerosis, acute aseptic arthritis, and type 1 diabetes mellitus after receipt of the vaccine dose and to compare this incidence with that occurring in an unvaccinated matched comparator group, and in two groups of individuals exposed to other types of COVID-19 vaccines (i.e., one viral vector vaccine comparator group vaccinated [i.e., Vaxzevria[®] {AZD1222}] by Oxford/AstraZeneca) and one mRNA vaccine comparator group (i.e., Comirnaty[®] [tozinameran] by Pfizer/BioNTech and Spikevax[®] [elasomeran] by Moderna).

As a sensitivity analysis for acute events, a cohort analysis (following the same approach used in the main analysis for non-acute events) will be conducted.

- **Exposed cohort:** individuals will have received at least 1 dose of Ad26.COV2.S vaccine.
- **Concurrent unexposed cohort:** individuals that have not been vaccinated with Ad26.COV2.S vaccine or any other COVID-19 vaccine at any time prior to the index date (time zero) matched to the vaccinated individual for important characteristics as described in Section 8.7.2.1.
- **Cohort exposed to other COVID-19 vaccines:** individuals will have received at least 1 dose of a viral vector COVID-19 vaccine (i.e., Vaxzevria[®] [AZD1222] by Oxford/AstraZeneca) or an mRNA COVID-19 vaccine (Comirnaty[®] [tozinameran] by Pfizer/BioNTech and Spikevax[®] [elasomeran] by Moderna, respectively).

A sensitivity analysis will compare the Ad26.COV2.S vaccine with the active comparators with 1) a 1-dose strategy and 2) a 2-dose strategy.

In this retrospective cohort design, the start of follow-up will be defined as the time when study outcomes start to be counted. The index date in the exposed cohorts (i.e., recipients of the vaccines)

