8.7. Data Analysis

Detailed methodology for summary and statistical analyses of data collected in this study will be documented in an SAP for the feasibility assessment and the respective SCRI and cohort safety analyses. All analyses will be conducted using R version R-4.0.3 or higher (Foundation for Statistical Computing, Vienna, Austria; <https://www.R-project.org>) or SAS version 9.3 software or higher (Cary, North Carolina, USA; SAS Institute, Inc.). The SAP will contain more detail about the analysis and data pooling and may modify the plans outlined in the protocol; any major modifications of primary endpoint definitions or their analyses would be reflected in a protocol amendment.

A general description of the planned statistical methods to be used to analyse the data collected in this study is presented in the following subsections. Additional details will be provided in the SAP. A summary of planned analyses is provided in [Table 5](#).

Table 5: Summary of Planned Analyses

Analysis	Acute AESIs Study design	Non-acute Study design for Non-acute AESIs	Risk window Definition of Risk window	Notes on the main purpose of analysis/difference from the primary analysis
Feasibility	Cohort	Cohort	none	Baseline characteristics, vaccine uptake, assessing the quality of data and of algorithms for outcomes and covariates, and the number of outcomes and time-to-event.
Primary (Final)	SCRI: post-vaccination control window	Cohort: exposed versus concurrent unexposed comparator and versus other COVID-19 vaccine exposed	Disease-specific risk window	SCRI: Using a pre and post-vaccination control window to assess the effect of the order of windows; Calculating and comparing the incidence rates of each AESI; Analysis of negative control data
Secondary (Final)	Subpopulation SCRI	Subpopulation cohort	Disease-specific risk window	Sub-population analysis
Sensitivity (Final)	Cohort: exposed versus concurrent unvaccinated comparator and/or versus other COVID-19–vaccine exposed	Cohort: exposed versus concurrent unexposed comparator and versus other COVID-19 vaccine exposed	Extended risk windows for acute events	Acute events: Compare different analytical approaches and incorporate the use of extended risk windows; Non-acute: not applicable

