8.7.1.2. Cohort Design**Demographic and Baseline Characteristics**

The distributions of baseline characteristics at index date by exposure group will be calculated to describe the study cohort and illustrate differences between the groups. For continuous variables, means, standard deviations, medians, and other quartiles will be estimated. For categorical variables, counts and proportions will be estimated. The missingness of variables will also be described. Comparative analyses will be included in the final report. Further details will be described in the SAP. To describe the relative imbalance of characteristics between exposed and unexposed groups, absolute standardised differences will be calculated for each baseline characteristic. Multilevel categorical variables will calculate an overall standardised difference across all levels. The larger the absolute standardised difference values, the greater the imbalance between baseline characteristics.

Measures of Occurrence and Association

Incidence rates for each AESI will be calculated by dividing the number of cases by the follow-up person-time. Poisson regression models will estimate incidence rate ratios and 95% CIs. Robust variance estimation will account for an individual's possibility to be included in the exposed and unexposed cohorts. The Poisson model for each AESI will include the number of events in each cohort as the dependent variable, the exposure status as the binary independent variable, and the natural logarithm of the person-time as the offset variable. The attributable risk will be computed as the difference between the incidence rate in the exposed cohort and the incidence rate in the unexposed cohort.

Adjustment for Baseline Imbalances

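### The cohort follow-up rule has no stop at the end of the AESI risk window, which contradicts the window-based objective and study size and, followed literally, dilutes the acute-event sensitivity cohort

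*Protocol*

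**What the plan says.** **The follow-up rule.** In Section 8.2.3, for the cohort, "the follow-up will start at the beginning of the vaccination risk window, as detailed in Table 1". It then "ends at the occurrence of each AESI, death, end of data availability, individual exits the database, after one year of follow-up". The rest of the list covers only censoring vaccinations: any COVID-19 vaccine for the unexposed, a different one for the exposed. One year is the only time limit. The Abstract repeats the rule: "follow-up starts at the start of each risk window and ends at the occurrence of each AESI, death, end of data availability", and so on to one year. By contrast, the SCRI bullet in Section 8.2.3 lists "end of the post-vaccination risk or control window, or receipt of another COVID-19 vaccine".

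**The rate.** Section 8.7.1.2: "Incidence rates for each AESI will be calculated by dividing the number of cases by the follow-up person-time".

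**Acute events in the cohort.** Section 8.1.2.2 gives acute events a sensitivity cohort analysis, "following the same approach used in the main analysis for non-acute events) will be conducted". In Table 1 every non-acute event has a window of 1-365 days.

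**What points the other way.**
- The primary objective in Section 7 makes the comparison "within disease-specific risk periods", and this covers the unexposed and active-comparator contrasts.
- The acute endpoints in Section 7 are incidences within stated day ranges, from 0-2 up to 1-60.
- Section 8.3.3.1 ascertains incidence inside the disease-specific windows.
- The Abstract and Section 8.7.1 plan AESI-specific windows after each dose of a two-dose comparator.
- Table 5 gives the acute-event cohort row the window entry "Extended risk windows for acute events".
- The footnote to Table 2 assumes 60 days of risk window per person.

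**The concern.** A follow-up rule fixes both the events counted and the person-time. A programmer who codes the Section 8.2.3 list as written, and then the rate in Section 8.7.1.2, would count acute AESIs for up to a year in both groups. Most of that year lies outside the risk period, so a short-lived excess is averaged with a long stretch of background risk.

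Section 8.1.3 uses the acute-event cohort to back up the SCRI where the SCRI has less power or is open to confounding by season. The cohort is also the only design that compares acute AESIs with unvaccinated people, which is part of the primary objective. A diluted cohort result beside a raised SCRI result could be read as the cohort failing to confirm the signal, when the two analyses had used different risk periods.

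Table 5 adds a smaller difficulty. The acute cohort row names extended windows and no row names the Table 1 window, so it is unclear whether the SCRI and the cohort are to be compared over the same period.

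**Working it through.** **1. Which person-time the study size assumes.** Table 2 is reproduced by a precision calculation with a true rate ratio of 1 and 1:1 groups. Expected events per group are A = 2 × (1.960 + 0.842)² / (ln U)², and N = A / (IR × 60/365). For an upper limit U = 3 and IR = 100 per 100,000 person-years:
- A = 15.70 / 1.207 = 13.006
- N = 13.006 / (0.001 × 60/365) = 79,121, the figure in the table

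All 16 cells reproduce to within one subject. With one year per person the same cell would be 13.006 / 0.001 = 13,006. The cohort was therefore sized on a 60-day window, not on one-year follow-up.

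**2. Dilution if the stop list is followed literally.** Let w be the window length in days, T the follow-up in days and RR the in-window rate ratio. With a constant background rate and no excess after the window:

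IRR observed = 1 + (RR − 1) × w / T

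The window lengths come from Table 1. The protocol gives no in-window RR for the cohort, so the RR values are assumptions, shown as a range. With T = 365:

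| In-window RR | 3 d | 14 d | 28 d | 42 d | 60 d |
|---|---|---|---|---|---|
| 1.5 | 1.00 | 1.02 | 1.04 | 1.06 | 1.08 |
| 2 | 1.01 | 1.04 | 1.08 | 1.12 | 1.16 |
| 3 | 1.02 | 1.08 | 1.15 | 1.23 | 1.33 |
| 5 | 1.03 | 1.15 | 1.31 | 1.46 | 1.66 |
| 10 | 1.07 | 1.35 | 1.69 | 2.04 | 2.48 |

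Example: RR 3 and 28 days give 1 + 2 × 28/365 = 1.15. Of the 29 acute rows in Table 1, 23 have windows of 28 days or less.

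**3. Earlier censoring.** With T = 180 days as an assumed mean, RR 3 gives 1.03, 1.16, 1.31, 1.47 and 1.67 for the same five windows.

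**4. Effect on power.** Take 100,000 per group (the minimum exposed cohort in Section 8.5.1, matched 1:1), 100 per 100,000 person-years, a 28-day window and RR 3.
- Within the window: 7.67 and 23.01 expected events, ln 3 = 1.099, SE = √(1/7.67 + 1/23.01) = 0.417, two-sided 5% power about 75%.
- Over one year: 100 and 115.3 expected events, ln 1.153 = 0.143, SE = 0.137, power about 18%.

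**5. A mixed reading.** Suppose cases are limited to the window, as the endpoints say, but the denominator runs to one year, as Section 8.7.1.2 says. The rate ratio is then roughly kept. Each rate, and the attributable risk in Section 8.7.1.2, falls by a factor of 365/w: 13 at 28 days and 6.1 at 60 days.

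**The case against.** The strongest reply is that the protocol does not ask for a full-year count of acute events. An event on day 200 is not an acute endpoint in Section 7. The objective, case ascertainment, comparator-dose windows and Table 2 all work within windows. The one-year limit fits the non-acute AESIs and can be read as a general maximum. On this view the list is incomplete drafting, and the analysts would apply the windows anyway.

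Much of this stands. A reader might infer from the list that acute cohort rate ratios will certainly be diluted, and almost to 1 for every acute AESI. The documents do not support that. Dilution follows only from the literal reading. Even then, RR 3 gives 1.23 to 1.33 for 42 to 60 days, and RR 10 gives 1.69 to 2.48 for 28 to 60 days. Exposed people are also censored at any further COVID-19 dose (Section 8.3.1), which shortens follow-up.

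Nor does Table 5 show that every acute AESI gets only an extended window. Sections 8.1.3, 8.7.6 and 8.9 reserve extension for events whose interval is not well established. If an extended window governs, the one-year formula does not apply: extending 28 days to an illustrative 42 or 60 turns RR 3 into 1 + 2 × 28/42 = 2.33 or 1 + 2 × 28/60 = 1.93.

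What does not stand is leaving the point to the SAP. The protocol states an explicit list of stops, names the window end for the SCRI and omits it for the cohort, and then defines the rate on that follow-up.

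**Conclusion.** The cohort stop list is wrong as written. It contradicts the window-limited objective, endpoints, case ascertainment, Table 5 and the 60-day basis of Table 2. The contradiction is certain from the text. The dilution is conditional on following Sections 8.2.3 and 8.7.1.2 literally.

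On that reading, an assumed in-window RR of 3 appears as about 1.02 to 1.15 for windows up to 28 days and 1.23 to 1.33 for 42 to 60 days. This rests on a constant background rate, no excess after the window and full one-year follow-up.

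The reach is limited to the sensitivity cohort for acute AESIs. The primary SCRI already stops at the window, and for non-acute AESIs the 1-365 day window matches the one-year limit, so no primary estimate changes.

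**What to change.** 1. In Section 8.2.3 and the Abstract, add to the cohort stop list for acute AESIs the end of the AESI-specific risk window (Table 1), or of the extended window where that analysis applies. Word it so that the planned windows after each comparator dose are kept. A single stop at the end of the first-dose window would remove the second-dose window.
2. In Section 8.7.1.2, state that cases and person-time are those within the risk window.
3. In Table 5, state that the acute-event cohort uses the Table 1 window, so that it matches the SCRI. List extended windows as an additional analysis for the AESIs whose risk interval is not well defined.

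The cost is a few phrases in three places, one table row and window-based start and end dates in the cohort code. No new data are needed, and Table 2 stays as it is.
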